13.4.5 Overall Survival

Defined as the time from registration to death due to any cause. The distribution of survival time will be estimated using the method of Kaplan-Meier [46]. Special attention will be paid to any registered patient who dies early (i.e., within 60 days) of initiating their treatment. Circumstances surrounding such early deaths will be classified as being either due to malignant disease, toxicity, other causes, or of unknown reasons.

13.4.6 Laboratory Correlative Studies

All analyses with respect to the translational component of this study are intended to be hypothesis-generating and descriptive in manner. For this study, we will investigate the effect of nivolumab on tumor burden by analyzing the clearance of plasma Epstein-Barr virus (EBV) DNA during the first 4-6 weeks of treatment. In addition, we will investigate the association between treatment outcome and the following immunological markers: Intratumoral expression of PD-1 and PD-L1 in archived NPC tissues, serum absolute lymphocyte count at baseline and post-treatment, expression of PD-1 in CD8+ T cells in tumor infiltrating lymphocytes (TIL) at baseline. Plasma EBV DNA half-life during the first 6 weeks of treatment will be correlated with RECIST-response to nivolumab.

The Chi-Square (or Fisher's Exact test) will be used to assess the association of categorical clinical data with categorical biomarker data. Time-to-event clinical data (PFS, OS) will be correlated with biomarker data using Kaplan-Meier methodology and Cox regression models. Logistic regression models will also be used to predict binary clinical data with baseline biomarker data. Finally, graphical methods and descriptive statistics will be used to summarize the data as well. Two-sided p-values < 0.05 will be considered statistically significant. For the functional MRI parameters, graphical methods and descriptive statistics will be used to assess the changes in these parameters over time. In addition, we will determine the associations between the MRI parameters and clinical endpoints like response and survival.

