2.4 Correlative Studies

Rationale for using plasma EBV DNA as a surrogate marker of tumor burden in NPC

Investigators at the CUHK pioneered the use of quantitative real-time-PCR to quantitate the level of plasma EBV DNA [24, 25]. It is a powerful prognostic marker which closely reflects tumor burden in NPC [26, 27]. Our investigators have also reported the kinetics of plasma EBV DNA during radiotherapy and surgery for NPC. An initial surge followed by a rapid drop in plasma EBV DNA level can be observed, with an estimated half-life of around 3.8 days (range 2.2-4.4 days) [25, 28]. Wang *et al.* found that the plasma EBV DNA clearance during the 1st 4 weeks of chemotherapy was prognostic, such that patients with a half-life of < 8 days were more likely to respond than those with longer half-life values [29]. Our experience with plasma EBV DNA half-life in a phase II study of a AKT inhibitor, MK-2206, suggested that patients with a drop in plasma EBV DNA levels were more likely to remain on treatment for 6 months or more, compared with those who did not experience with a drop in level [30].

In a recently published study which compared the detection capability of this marker across different laboratories in Stanford University (USA), Taiwan and the CUHK, the Hong Kong site

was found to have one of the highest detection sensitivity (93%) [31]. This study also serves to harmonize the plasma EBV DNA assay in preparation for an international NRG study (NRG-HN001, NCT02135042). This study aims to individualize adjuvant chemotherapy using plasma EBV DNA in locoregionally advanced NPC, and involves investigators from the NRG, Chinese University of Hong Kong and Taiwan.

Rationale for measuring PD-L1 expression in tumor and immune cells

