9.2 Exploratory/Ancillary Correlative Studies

9.2.1 Plasma EBV DNA Clearance

9.2.1.1 Hypothesis: We hypothesize that plasma EBV DNA half-life during the first 6 weeks of treatment may be associated with subsequent RECIST-response to nivolumab.

9.2.1.2 Collection of Specimen(s):

This test is **mandatory** for all enrolled subjects. 3-5ml of EDTA blood sample (x 1 tube) will be taken at baseline (within 7 days of starting the first dose of study drug), and then at weekly interval: week 1 (day 7 +/- 2 days), week 3 (day 21 +/- 2 days), week 4 (day 28 +/- 2 days), week 5 (day 35 +/- 2 days) and week 6 (day 42, +/- 2 days). Week 2 sampling is omitted given the possibility of a surge in level. Consecutive samples can only be taken with no more than 5 to 9 days apart.

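### EBV DNA half-life is named as the predictor of response but has no usable value when levels are flat or rising; the log-linear slope avoids this at almost no cost

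*Combined protocol and SAP*

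**What the plan says.** The hypothesis is in Section 9.2.1.1: "We hypothesize that plasma EBV DNA half-life during the first 6 weeks of treatment may be associated with subsequent RECIST-response to nivolumab". Section 13.4.6 turns it into an analysis: "Plasma EBV DNA half-life during the first 6 weeks of treatment will be correlated with RECIST-response to nivolumab".

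Section 9.2.1.2 schedules plasma at baseline and around days 7, 21, 28, 35 and 42, with this reason for the gap: "Week 2 sampling is omitted given the possibility of a surge in level".

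Section 2.4 gives two pieces of background. In another group's chemotherapy study, "patients with a half-life of < 8 days were more likely to respond than those with longer half-life values". In the investigators' own earlier phase II study of a targeted agent, patients whose level dropped were more likely to stay on treatment for six months or more, "compared with those who did not experience with a drop in level".

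The documents do not say how half-life is calculated, or how flat, rising or undetectable levels enter the analysis. Section 13.4.6 adopts no half-life cut-off. The model it names for binary outcomes is worded for baseline markers only: "Logistic regression models will also be used to predict binary clinical data with baseline biomarker data". Half-life is an on-treatment measure, so the method of correlation is open too. The section calls all translational work hypothesis-generating and descriptive, yet also sets a test level: "Two-sided p-values < 0.05 will be considered statistically significant".

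**The concern.** Half-life describes decay. It works where nearly every patient's level falls, as expected during radiotherapy or after surgery. Here the design discriminates a 20% from a 5% response rate, so most patients are expected not to respond, and some will probably have flat or rising EBV DNA. The protocol itself has met patients without a drop.

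For these patients the planned predictor is infinite or negative. The analyst must then do one of three things:

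- use the signed value, which puts a rising patient on the wrong side of every clearing patient;
- exclude the patient, which removes a group that is probably mostly non-responders;
- adopt a rule, possibly after responses are known.

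The result of the half-life/response analysis can depend heavily on that unstated choice.

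**Working it through.** The plan gives no expected half-life, effect size or power for this analysis, so there is no figure of its own to reproduce.

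**Step 1: the measure itself.** With slope k per day from log EBV DNA on time, half-life = −ln 2 / k. For a week-6/baseline ratio r over 42 days, k = ln(r)/42. For example, r = 0.10 gives k = −2.303/42 = −0.0548 and half-life = 0.693/0.0548 = 12.6 days.

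| Week-6/baseline ratio | Half-life (days) |
|---|---|
| 0.01 | 6.3 |
| 0.10 | 12.6 |
| 0.50 | 42 |
| 0.99 | 2,897 |
| 1.00 | infinite |
| 1.01 | −2,926 |
| 2 | −42 |
| 10 | −12.6 |
| 100 | −6.3 |

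The value jumps from large positive to large negative as the slope crosses zero. Every rising patient lies below every clearing patient, so a ranking by signed half-life places all of them ahead of the fastest clearer. This needs no assumption about the data.

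**Step 2: how much it could matter.** Inputs from the documents are 35 evaluable patients (13.1.3) and the 20% target response rate (13.1.5), so 0.20 × 35 = 7 responders. Assumed inputs, in log2 units per week, are a responder mean slope of −0.7, a non-responder mean varied from +0.2 to −0.4, and SD 0.5 in both groups. On this scale half-life in days is −7/slope. Mean AUC for response over 4,000 simulated samples per row:

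| Non-responder mean slope | Patients rising | Slope | Half-life, risers ranked slowest | Half-life, risers dropped | Raw half-life |
|---|---|---|---|---|---|
| +0.2 | 54% | 0.90 | 0.89 | 0.81 | 0.32 |
| 0.0 | 42% | 0.84 | 0.83 | 0.77 | 0.42 |
| −0.2 | 29% | 0.76 | 0.76 | 0.71 | 0.50 |
| −0.4 | 18% | 0.66 | 0.66 | 0.63 | 0.53 |

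In the first row about 97% of the rising patients are non-responders.

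**Step 3: a second set of assumptions.** This uses the planned sampling days, log-scale noise SD 0.3, between-patient slope SD 0.04 per day and a responder mean of −0.08 per day. The share of non-responders truly rising is set at 10, 30, 50 and 70%:

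| Non-responders rising | Slope | Risers dropped | Raw half-life | Share of the 35 lost if risers dropped |
|---|---|---|---|---|
| 10% | 0.69 | 0.67 | 0.61 | 9% |
| 30% | 0.85 | 0.81 | 0.57 | 25% |
| 50% | 0.92 | 0.86 | 0.44 | 41% |
| 70% | 0.96 | 0.90 | 0.29 | 56% |

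In every scenario slope does best, dropping rising patients costs some discrimination and raw half-life is worst. An AUC below 0.5, meaning a reversed association, appears only when rising levels are common.

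**The case against.** The plan says only that half-life will be correlated with response. It does not say that signed values will be ranked or that rising patients will be excluded. In the earlier study described in Section 2.4, patients without a drop were kept and formed the less favourable comparison group, so a sensible analyst may well treat them as slow clearers here. Among decliners, half-life is a monotone transform of slope and the ranks are identical. Once rising patients are ranked slowest, the AUC is 0.89 against 0.90 for slope. On this view one sentence on handling is all that is missing. All of this stands, and it limits the claim to what happens if the plan is followed literally. It does not remove the point, because that handling is nowhere specified.

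Slope has limits of its own. A single straight line is an approximation if there is an early surge, and log EBV DNA is undefined when the level is undetectable. Both are fair, and the second needs its own rule.

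A reader might infer three stronger claims that the documents do not support:

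- **That rising patients will meet an 8-day cut.** That cut is background in Section 2.4, and Section 13.4.6 does not adopt it.
- **That objective 1.3.1 fails.** That objective concerns the effect of nivolumab on tumor burden through EBV DNA clearance. Section 13.4.6 lists it separately from the half-life/response correlation, whose hypothesis is in 9.2.1.1.
- **That the association will reverse.** This depends on the assumed slopes. With 10% of non-responders rising, raw half-life still gives an AUC of 0.61.

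**Conclusion.** The point holds as a cheap improvement to an exploratory analysis. That half-life has no finite value at zero slope and changes sign beyond it is arithmetic. That some patients will not decline is made likely by the protocol's own experience. The plan names the measure without a rule for those patients.

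The size is illustrative. AUC is 0.66–0.90 with slope, 0.63–0.81 with rising patients dropped and 0.32–0.53 with raw half-life, when 18–54% of patients rise. These figures rest on assumed slope distributions and 7 responders among 35, and the documents give no data on how many patients will rise. The order of the three approaches was the same in every scenario run; the size of the gaps was not.

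The consequence is confined to the half-life/response analysis of Section 9.2.1.1. The primary endpoint, the interim rule and the final decision rule do not use EBV DNA.

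**What to change.** Amend Section 13.4.6, and Section 9.2.1.1 to match:

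1. Make the predictor each patient's least-squares slope of log EBV DNA per week, from baseline to week 6.
2. State the substitution for undetectable values, for example the assay detection limit.
3. Report half-life descriptively, for patients with a negative slope only.
4. Class patients with slope ≥ 0 as slowest clearance in any ranking or cut.

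The cost is SAP wording, with the same samples and the same assay. The drawbacks are small: the straight line is approximate if levels surge early, and comparison with published half-lives is limited to decliners.

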4.4 Screening and General Guidelines

Following registration, patients should begin protocol treatment \leq 21 days. Issues that would cause treatment delays should be discussed with the Principal Investigator. If a patient does not receive protocol therapy following registration, the patient's registration on the study may be canceled. The Study Coordinator should be notified of cancellations as soon as possible. After the consent form is signed, refer to section 10 'Study Calendar' for screening procedures. Standard contrast CT will be done for assessing non-local recurrences. MRI will be used for assessing local recurrence. If dual PET and contrast CT is used to assess non-local recurrences at baseline, all subsequent radiological assessments must include a PET-CT.

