13.4 Analysis of Secondary Endpoints

This study will assess multiple secondary endpoints, including adverse events, tumor response to nivolumab based on immune-related response criteria (IRC), duration of response, progression-free survival (PFS), overall survival (OS), and laboratory correlates. The analysis population for these endpoints will be the same as that for the primary endpoint – i.e., all patients meeting the eligibility criteria who have signed a consent form and have begun treatment.

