13.4.4 Progression-Free Survival (PFS)

Defined as the time from registration to the first of either death due to any cause or progression. The distribution of PFS will be estimated using the method of Kaplan-Meier [46].

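### Section 13.4.6 relates post-baseline markers to PFS and OS counted from registration with no landmark, which exposes these exploratory analyses to guarantee-time bias

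*Combined protocol and SAP*

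**What the plan says.** **Clock.** Section 13.4.4 sets PFS as "Defined as the time from registration to the first of either death due to any cause or progression", and Section 13.4.5 sets OS as "Defined as the time from registration to death due to any cause". Section 4.4 ("Following registration, patients should begin protocol treatment") allows up to 21 days between registration and first dose, and marker weeks run from first dose.

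**Population.** Section 13.4 lists laboratory correlates among the secondary endpoints and says "The analysis population for these endpoints will be the same as that for the primary endpoint". That means every eligible, consented patient who started treatment, not those event-free when a marker is taken.

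**Method.** Section 13.4.6: "Time-to-event clinical data (PFS, OS) will be correlated with biomarker data using Kaplan-Meier methodology and Cox regression models". The sentence after it is narrower: "Logistic regression models will also be used to predict binary clinical data with baseline biomarker data". Only the logistic models carry a baseline restriction.

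**Post-baseline markers.**
- Lymphocyte count: Section 13.4.6 relates treatment outcome to "serum absolute lymphocyte count at baseline and post-treatment", with no post-treatment time point given.
- Functional MRI: Section 13.4.6 plans associations with survival. The Study Calendar puts scans at baseline and weeks 3, 6, 8 and 16.
- EBV DNA: the specific analysis is "Plasma EBV DNA half-life during the first 6 weeks of treatment will be correlated with RECIST-response to nivolumab". It reaches PFS and OS only through the general sentence.

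The documents contain no landmark, no time-dependent covariate, and no rule for a patient whose event comes before the marker is measured. Section 13.4.6 describes the translational analyses as exploratory but sets a two-sided 0.05 threshold for calling a result significant.

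**The concern.** A marker read at week 8 or 16 exists only for patients still under observation then. If it enters a Kaplan-Meier or Cox analysis that starts at registration, it is treated as known from time 0. Patients who fail early cannot belong to the favourable group, so that group is guaranteed event-free time up to the measurement. A marker with no prognostic value can then appear protective, always in the same direction.

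The lymphocyte count is the plainest case. The Study Calendar ties on-treatment differentials to re-dosing, and Section 5.3 generally stops treatment at progression, so whether a later value exists depends partly on outcome. Section 2.4 cites a rise at about two months in an ipilimumab study as a possible predictor and says further validation here is warranted. At stake is which marker hypotheses are carried forward from this trial.

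**Working it through.** The plan gives no figure for these analyses, so there is nothing of its own to reproduce. The size below is illustrative.

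**Inputs.** 35 evaluable patients (Section 13.1.3). Median PFS of 4.4 or 2.7 months, borrowed from the median times to progression of the two earlier studies in Section 13.1.1. Median OS of 12 to 15 months, a proxy from Section 2.1. Exponential times are assumed.

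**Step 1: share of patients with an event before the marker.** The formula is 1 − 2^(−t/m), with t in months = weeks × 12/52.18 and m the median. Week 8 is 1.84 months and week 16 is 3.68 months.
- PFS, m = 4.4: 1 − 2^(−1.84/4.4) = 25% by week 8; 1 − 2^(−3.68/4.4) = 44% by week 16.
- PFS, m = 2.7: 38% and 61%.
- OS, m = 12 to 15: 8 to 10% and 16 to 19%.

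At m = 4.4 that is 35 × 0.252 ≈ 9 patients by week 8 and 35 × 0.440 ≈ 15 by week 16.

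**Step 2: null simulation.** The marker is unrelated to outcome, half of measured patients are favourable, and the test is two-sided at 0.05. The plan states no handling of unmeasured patients, so each row is an assumption. PFS, median 4.4 months, clock from registration:

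| Handling | Week 8: false positives (HR) | Week 16: false positives (HR) |
|---|---|---|
| Early failures counted unfavourable; progression seen continuously; no dosing delay | 25–26% (0.58) | 53–57% (0.41) |
| Same, first dose 0–3 weeks after registration | 33% (0.54) | 61% (0.38) |
| Early failures counted unfavourable; progression recorded only at scheduled scans | about 8–11% (0.74–0.76) | about 49% |
| Any rise at 2-weekly draws (assumed 15% chance per draw), 0–3 week delay | 17% (0.66) | 60% (0.44) |
| Only patients measured at the fixed time, 0–3 week delay | 6% (1.03) | 7% (0.99) |

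The scheduled-scan row adds deaths on a 12-month median and does not model symptomatic deterioration. With median PFS 2.7 months, the second row becomes 49% and 70%. For OS, counting early failures as unfavourable gives 12 to 13% at week 8 (HR 0.68) and 23 to 29% at week 16 (HR 0.50 to 0.52).

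**Step 3: with a landmark.** Restarting the clock 3 weeks after the nominal marker week among event-free patients gives about 4 to 9% false positives across all settings. Hazard ratios are 0.86 to 1.03; the 0.86 comes from the sparse week-16 any-rise case at median 2.7 months.

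**Step 4: what remains when only measured patients are compared.** The hazard ratio is close to 1, but every curve stays at 100% until the marker time. Under the exponential model, median PFS from registration among patients measured at week 16 is 3.68 + 4.4 = 8.1 months, against a true 4.4. At week 8 it is 1.84 + 4.4 = 6.2 months.

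**The case against.** The strongest reply is that the distorting rule is not in the plan. Nothing says that a patient without a post-baseline value is counted as unfavourable. EBV half-life and the MRI parameters are continuous and need real measurements, so such a patient would naturally be missing. Everyone compared then shares the same guaranteed period and the hazard ratio is nearly unbiased. This stands, and it is why the plan is exposed to the bias rather than certain to have it. It does not rescue the Kaplan-Meier levels, and Section 13.4 points to the full treated population rather than to measured patients.

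Second, the first response scan is at week 8 (Section 11.1), and week-8 MRI falls at the same visit where possible. Scheduled progression therefore cannot precede a week-8 marker; only deaths, symptomatic deterioration or unscheduled progression can. This also stands, and it is why the week-8 range starts near 8%.

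Third, a reader might infer that the week-16 figures describe the MRI analysis. They assume 35 patients. The MRI sub-study is optional, open to one site, and relates imaging to survival only if enough patients take part (Sections 9.2.2.1 and 9.2.2.2).

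Fourth, a reader might infer that EBV clearance is expressly planned against PFS and OS. The documents tie it explicitly only to RECIST response.

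Fifth, the two-month lymphocyte rise is background, and Section 9.1.2 relates the baseline count to response. But Section 13.4.6 does name the post-treatment count for association with treatment outcome, so that leg remains.

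**Conclusion.** The omission is real: registration clock, all treated patients, post-baseline markers in scope, and nothing to align the clock with the measurement. It exposes the exploratory PFS and OS analyses to guarantee-time bias.

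For PFS with median 4.4 months and 35 patients, counting early failures as unfavourable gives roughly 8 to 26% false positives at week 8 (33% if the registration-to-dose gap is included) and about 50 to 60% at week 16. An any-rise definition causes the same kind of error. Comparing only patients measured at one fixed time gives about 5 to 8% and leaves only the absolute curves inflated. These sizes rest on exponential times, medians borrowed from other studies, and handling rules the plan does not state.

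It would be too strong to conclude that the plan builds in a biased hazard ratio, because that depends on an unstated choice. Nor is the trial's main conclusion at risk: the primary endpoint is a confirmed response rate, and no interim, safety or go/no-go decision uses these correlates. The exploratory label limits the consequence but does not remove a bias that runs one way, particularly with a 0.05 significance threshold attached.

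**What to change.** Amend Section 13.4.6 so that, for each post-baseline marker:
- the measurement time is fixed in advance, including one for the post-treatment lymphocyte count;
- PFS and OS start at a landmark at the end of that marker's measurement window, counted from first dose so that the gap of up to 21 days after registration is allowed for, among patients still at risk; or the marker enters a Cox model as a time-dependent covariate;
- the number excluded, and why (earlier event, censored, not measured), is reported.

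Keep registration as time 0 for baseline markers. State whether progression found at the same visit as the marker counts as before the landmark.

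This needs only wording and no new data. The cost is that patients with an event before the landmark leave that analysis. Adding the full 3-week gap, the exponential model puts 28 to 41% of PFS events before week 9 (a week-6 marker) and 50 to 67% before week 19 (a week-16 marker). For OS the shares are 9 to 11% and 18 to 22%. Week-16 PFS may be too sparse for inference, and the plan should say so beforehand.

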Topalian *et al.* found that high level of tumoral expression of PD-L1 was associated with higher response duration in nivolumab-treated patients [23]. But this was not observed in a nivolumab-ipilimumab study in melanoma [8]. Our preliminary work has shown that 15/20 NPC tumors (75%) expressed PD-L1, thus we plan to validate this marker in this study. The dynamic nature of tumoral PD-L1 expression may be dependent upon changes in the tumor microenvironment, and is closely correlated with the degree of immune infiltrate in tumors [32]. More recently in a phase 1b study of another PD-1 inhibitor, MK-3475 in recurrent head and neck squamous carcinoma, patients with tumors that overexpressed PD-L1 above an arbitrary cut-off point (Roche/Genentech assay used, defined as PD-L1 expression in $\geq 1\%$ of both tumor and adjacent immune cells) had higher tumor response rate (45.5%) than those who did not (11.4%) [33]. Based on these data, therefore, PD-L1 expression in the TILs in tumors will also be measured in this study. A recently published study has shown that the EBV oncogenic protein, latent membrane protein-1 (LMP-1) could up-regulate PD-L1 through STAT3, AP-1 and NF- κ B pathways in NPC cell lines. IFN- γ could also up-regulate PD-L1 independent of but synergistic with LMP1 in vitro [42].

Rationale for measuring absolute lymphocyte count

A study on ipilimumab has shown that an absolute lymphocyte count (ALC) of $> 1,000/\text{mL}$ and an increase in ALC around 2 months after treatment may predict clinical benefit [12]. But this was not observed in a nivolumab-ipilimumab study [8]. Further validation in this study is warranted.

Rationale for the functional MRI study

Discussed in section 9.2.2.1.

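### Baseline plasma EBV DNA, described as strongly prognostic and sampled in every patient, has no stated role in the exploratory biomarker models for PFS and OS

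*Combined protocol and SAP*

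**What the plan says.** Section 13.4.6 (Laboratory Correlative Studies) states that "Time-to-event clinical data (PFS, OS) will be correlated with biomarker data using Kaplan-Meier methodology and Cox regression models". The immunological markers it lists are intratumoral PD-1 and PD-L1, absolute lymphocyte count, and PD-1 in CD8+ tumor-infiltrating lymphocytes. It names no covariate for any model and does not say whether the Cox models are univariable.

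EBV DNA enters that section only as clearance over the first 4 to 6 weeks and as a half-life. The only outcome named for the half-life is RECIST response.

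Section 2.4 says of plasma EBV DNA: "It is a powerful prognostic marker which closely reflects tumor burden in NPC". Section 9.2.1.2 makes the test mandatory for all enrolled subjects and specifies that "3-5ml of EDTA blood sample (x 1 tube) will be taken at baseline", within 7 days of the first dose. The Study Calendar (section 10) repeats that sampling is mandatory.

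On the status of these analyses, section 13.4.6 says both that "All analyses with respect to the translational component of this study are intended to be hypothesis-generating and descriptive in manner" and that "Two-sided p-values < 0.05 will be considered statistically significant".

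**The concern.** The plan identifies a strong prognostic variable, measures it before treatment in everyone, and gives its level no place in the models for PFS and OS. Two consequences follow.

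- **Precision.** Omitting a strong prognostic covariate from a Cox model pulls a true marker effect toward the null and lowers power. This needs no correlation between the marker and EBV DNA.
- **Possible confounding.** The trial has one arm, so no control group helps to separate a marker that predicts benefit from nivolumab from one that only tracks tumor burden. If a marker correlates with EBV DNA level, its unadjusted association with PFS or OS partly reflects burden. Section 2.4 offers a qualitative reason to consider this for PD-L1, since "latent membrane protein-1 (LMP-1) could up-regulate PD-L1 through STAT3, AP-1" and other pathways in cell lines.

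Objective 1.3.2 asks which immune markers go with outcome. False leads and missed leads both weaken the answer. Because covariates are not named, the choice to adjust could also be made after the results are seen.

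**Working it through.** The plan gives no power, event count or effect size for the biomarker analyses, so there is no stated figure to reproduce. The power statement in section 13.1.5 concerns the response rate only.

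**Inputs from the documents**
- 35 evaluable patients (13.2.1).
- Accrual of about 20 months and at least 6 months of follow-up for the last patient (13.2.2), so follow-up ranges from 6 to 26 months.
- Median time to progression of 4.4 and 2.7 months in the two reference studies (13.1.1).
- PD-L1 positive in 15/20 = 75% of pilot tumors (2.4).
- Two-sided 0.05 (13.4.6).

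**Assumptions, not in the documents**
- Median PFS 4 months, exponential.
- EBV DNA HR 1.5 or 2.0 per SD.
- Marker–EBV DNA correlation 0, 0.3 or 0.5 (on the latent scale for a binary marker).
- True marker effect: HR 1.8 per SD (continuous) or HR 0.5 (binary).

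**Expected events.** With λ = ln 2/4 = 0.1733 and censoring uniform on 6 to 26 months, the censored fraction is (e^(−6λ) − e^(−26λ))/(20λ) = (0.3535 − 0.0110)/3.466 = 0.099. Events = 35 × 0.901 = 31.5. Variation in risk from EBV DNA lowers this to about 30 to 31 in the simulations.

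**Limit set by sample size.** Schoenfeld power is Φ(√(d·p(1−p))·|ln HR| − 1.96). With d = 30 and HR 0.5:
- 75/25 split: Φ(√5.625 × 0.693 − 1.96) = Φ(−0.32) = 38%.
- 50/50 split: Φ(√7.5 × 0.693 − 1.96) = Φ(−0.06) = 48%.

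The HR detectable with 80% power is 0.31 and 0.36 respectively.

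**Simulation.** Trials of 35 patients were analyzed by Cox regression, marker alone against marker plus EBV DNA, with a Wald test at 1.96. There were 3,000 trials per scenario for a continuous marker and 1,500 for a binary one.

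Rejection rate when the marker has no effect (unadjusted):

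| Marker | EBV HR 1.5, corr. 0.3 / 0.5 | EBV HR 2.0, corr. 0.3 / 0.5 | Adjusted, all four |
|---|---|---|---|
| Continuous | 9% / 17% | 13–15% / 32% | 5–6% |
| Binary, 75% positive | 6% / 10% | 7% / 14% | 6–7% |
| Binary, 50% positive | 8% / 12% | 11% / 22% | 6–7% |

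For the binary null marker, the unadjusted median HR is 1.16 to 1.31 at correlation 0.3 and 1.35 to 1.57 at 0.5. Adjusted, it is 0.94 to 1.00. At zero correlation there is no false association (unadjusted HR 0.99 to 1.01).

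Power when the marker has an effect and no correlation with EBV DNA (unadjusted → adjusted):

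| Marker | EBV HR 1.5 | EBV HR 2.0 |
|---|---|---|
| Continuous, HR 1.8 per SD | 76% → 81% | 65% → 79% |
| Binary, 75% positive, HR 0.5 | 31% → 37% | 27% → 35% |
| Binary, 50% positive, HR 0.5 | 35% → 43% | 29% → 42% |

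The gains are 5 to 14 points. Repeat runs moved individual cells by a few points, so about 4 to 15 is a fair range.

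Positive correlation can also hide a real effect. A protective binary marker with true HR 0.5 appears as 0.63 to 0.88 unadjusted, with power 8% to 21% against 33% to 42% adjusted. A negative correlation would bias the association in the opposite direction. OS was not simulated.

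**The case against.** A reader might infer that the plan excludes EBV DNA, that the marker effects are confounded, and that EBV clearance is to be modeled against PFS and OS. The documents support none of these.

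- Section 13.4.6 is silent on covariates. It does not declare the models univariable or rule EBV DNA out.
- No correlation between plasma EBV DNA level and PD-L1, PD-1 or lymphocyte count is reported. The LMP-1 finding concerns expression in cell lines, whereas plasma EBV DNA is said to reflect burden. Section 2.1 calls EBV ubiquitous in undifferentiated NPC in endemic regions, and section 2.4 says that IFN-γ raises PD-L1 independently of LMP-1. The tissue may be archived, while the plasma sample is taken within 7 days of the first dose. A correlation of 0.3 to 0.5 is therefore an assumption.
- For EBV half-life, the only outcome named is RECIST response. Use against PFS or OS is at most an inference from the general term for biomarker data.

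Three further arguments have weight. Objective 1.3.2 asks about association, and a marker that tracks burden really is associated with PFS; rejection is a false lead only if the question is the marker's effect beyond burden. The analyses are declared hypothesis-generating and claim no power. The IHC markers are dichotomized, which makes the gain smaller than for a continuous marker.

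These arguments lower the importance of the point but do not remove it. The loss of precision needs only that EBV DNA be prognostic, which section 2.4 asserts. The same section that calls the work descriptive also sets a significance threshold, so associations will be labeled significant or not. Reporting both models answers both forms of the question.

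**Conclusion.** The point holds as a minor one. Baseline plasma EBV DNA is called strongly prognostic, is available in everyone, and has no stated role in the PFS and OS models. Omitting it costs about 4 to 15 points of power when the marker is unrelated to it. If a marker correlates with it at 0.3 to 0.5, unadjusted null rejection is about 9% to 32% for a continuous marker, 6% to 14% for a binary marker at 75% prevalence, and 8% to 22% at 50% prevalence. Adjustment brings these to about 5% to 7%. All of these figures rest on the assumed EBV DNA hazard ratios and correlations and on about 30 PFS events.

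Confounding is a risk, not a demonstrated fact, and the documents give no ground for requiring the adjusted model as the main estimate. Small N is the larger limit: even adjusted, power for a binary marker with HR 0.5 stays at or below about 43%. The primary endpoint, interim rule and final rule are unaffected.

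**What to change.** In section 13.4.6:

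1. For each baseline marker, pre-specify a Cox model for PFS and for OS with the marker plus log10 baseline plasma EBV DNA, reported beside the marker-only model.
2. List baseline plasma EBV DNA itself as a marker.
3. If EBV clearance is modeled against any outcome, adjust for the baseline level.
4. Set undetectable baselines to the assay detection limit, without a separate indicator. If the 93% detection sensitivity in section 2.4 applied here (an assumption), 35 × 0.07 = 2.45 patients would be undetectable on average. The chance of 0 or 1 such patients would be 0.93^35 + 35 × 0.07 × 0.93^34 = 0.079 + 0.208 = 29%, so an indicator would often rest on one patient or none.

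The cost is a few lines of text and one degree of freedom in each model, with about 30 PFS events and fewer deaths for OS. No new sample or visit is needed.
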